**Research Hypothesis:**

Treatment with BMS-986237 will demonstrate no clinically relevant differences in safety relative to nivolumab and ipilimumab administered sequentially in patients with renal cell carcinoma.

**Schedule of Analyses:**

The incidence of AEs in the Broad Scope MedDRA Anaphylactic Reaction SMQ occurring within 2 days after dosing during the combination, Part 1 period is the primary endpoint for this study. The first (primary) analysis will be carried out for primary endpoint, safety-related secondary, and PK-related secondary endpoints when all participants who are still on-treatment complete Part 1 period. The final analysis will be carried out for efficacy-related secondary endpoints when all patients have at least 9 months of follow-up. Safety-related exploratory endpoints will also be analyzed at the time of both first (primary) analysis and final analysis. Efficacy-related exploratory endpoints will be analyzed at the time of the final analysis if data are available.

The duration of the study

- from start of randomization to primary analysis of the study is expected be approximately 9 months (6 months of accrual plus an additional 3 months to ensure all subjects who are still on-treatment have completed Part 1 period)
- from start of randomization to final analysis of the study is expected be approximately 15 months (6 months of accrual plus an additional 9 months of minimum follow-up to ensure all patients have at least 9 months of follow-up).

Subsequent descriptive analyses may be performed to summarize additional safety and survival data and to incorporate tumor assessment data captured beyond the primary and secondary endpoint analyses. Additional survival analysis may be conducted for up to 5 years beyond analysis of the primary endpoint.

## **2 STUDY DESCRIPTION**

### **2.1 Study Design**

This is a Phase II, open-label, randomized 2-arm study of the fixed ratio combination (BMS-986237) of nivolumab and ipilimumab in a 3:1 ratio (nivolumab 3 mg/kg and ipilimumab 1 mg/kg) in subjects with previously untreated advanced or metastatic RCC.

Subjects meeting all eligibility criteria will be randomized 1:1 ratio and stratified by IMDC prognostic score (0 vs 1-2 vs 3-6) to Arm A (BMS-986237) or Arm B (nivolumab and ipilimumab administered sequentially).

In Part 1, Arm A, BMS-986237 will be administered as one 60-minute infusion, every 3 weeks for up to 4 doses.

In Part 1, Arm B, nivolumab and ipilimumab will be administered sequentially within the same day, as two separate infusions, one 60-minute nivolumab infusion and one 30-minute ipilimumab infusion with a 30-minute break between each infusion, every 3 weeks for up to 4 doses.

Six weeks after the last dose in Part 1, subjects will then receive nivolumab 480 mg flat dose infused over 30 minutes every four weeks in Part 2 until progression or unacceptable toxicity.

Safety of subjects will be monitored on an ongoing basis by the study team. The BMS medical monitor is a physician who is responsible for reviewing the safety of patients in this study in a systematic and continuous manner. This includes a review of serious and non-serious adverse events including all hematological and non-hematological events.

[figure not shown]
In addition, study safety is evaluated on an ongoing basis by representatives of BMS Global Pharmacovigilance and the BMS medical safety team (MST), who operate independently from the clinical team and monitor safety across all nivolumab protocols, identify potential safety signals, notify appropriate stakeholders of relevant findings, and implement risk management plans.

The study population for this trial will include adult subjects ( $\geq 18$  years) with histological confirmation of RCC with a clear-cell component.

Subjects who advance to Part 2 will be treated until progression or unacceptable toxicity.

The study design schematic is presented in [Figure 2.1-1](#).

**Figure 2.1-1: Study Design Schematic**

\*6 weeks from last combination dose in Part 1 to first nivolumab monotherapy dose in Part 2

\*\*Treatment beyond initial investigator-assessed RECIST 1.1-defined progression will be considered in subjects experiencing investigator assessed clinical benefit and tolerating study therapy. Such subjects must discontinue therapy when further progression is documented.

## 2.2 Treatment Assignment

After the subject’s initial eligibility is established and informed consent has been obtained, the subject must be enrolled into the study by accessing an Interactive Response Technologies web-based system (IRT) to obtain the subject number. All subjects will be centrally randomized or using an Interactive Response Technology (IRT). Before the study is initiated, each user will receive log in information and directions on how to access the IRT.

Every subject that signs the informed consent form must be assigned a subject number in IRT. The investigator or designee will register the subject for enrollment by following the enrollment procedures established by BMS. The following information is required for enrollment:

- Date that informed consent was obtained
- Date of birth
- Gender at birth.

Once enrolled in IRT, enrolled subjects that have met all eligibility criteria will be ready to be randomized through the IRT. The following information is required for subject randomization:

- Subject number
- Date of birth
- IMDC prognostic score (0 vs 1-2 vs 3-6)

Subjects meeting all eligibility criteria will be randomized 1:1 ratio and stratified by IMDC prognostic score (0 vs 1-2 vs 3-6) to Arm A (BMS-986237) or Arm B (nivolumab and ipilimumab administered sequentially).

The randomization procedures will be carried out via permuted blocks within each stratum.

### 2.3 Blinding and Unblinding

This is an open-label study.

### 2.4 Protocol Amendments

This SAP incorporates the following amendments:

**Table 2.4-1: Protocol Amendments**

Amendment	Date of Issue	Summary of Major Changes
Revised Protocol 01 (Incorporates Amendment 01 and Administrative Letter 01)	18-JAN-2017	Incorporate additional safety parameters and clarifications as per the FDA guidance following the submission of IND 132265 . Clarify inconsistencies in the original protocol as per the review of local Ethical Committees. Correct typo errors on the original protocol Delete one of the eligibility criteria in the protocol synopsis (and align it with the text in the eligibility criteria section of the protocol body ) that was erroneously included in the original protocol.
Revised Protocol 02	2-AUG-2017	Adding clarifications to the protocol Correcting inconsistencies and text that was erroneously deleted in the Revised Protocol 01.

## 3 OBJECTIVES

### 3.1 Primary

The primary objective is to evaluate the difference in safety between co-administered FRC nivolumab 3 mg/kg and ipilimumab 1 mg/kg relative to sequentially administered nivolumab 3 mg/kg and ipilimumab 1 mg/kg as measured by the incidence of AEs in the Broad Scope MedDRA Anaphylactic Reaction SMQ occurring within 2 days after dosing during the combination, Part 1.

### 3.2 Secondary

- To evaluate incidence of AEs in the Narrow Scope MedDRA Anaphylactic Reaction SMQ
- To evaluate drug-related Grade 3 - 5 AE incidence rate defined using National Cancer Institute Common Terminology Criteria for Adverse Events (NCI CTCAE) version 4.0 criteria
- To evaluate causality Grade 3 - 5 AE incidence rate defined using NCI CTCAE version 4.0 criteria
- To determine PK comparisons of nivolumab and ipilimumab administered as FRC to that of sequentially administered nivolumab and ipilimumab

- To evaluate the objective response rate (ORR), as determined by investigators
- To evaluate progression free survival (PFS)

## 4 ENDPOINTS

### 4.1 Primary Endpoint: MedDRA Anaphylactic Reaction Broad Scope SMQ AE Incidence Rate

The primary endpoint of the study is the incidence of AEs in the Broad Scope MedDRA Anaphylactic Reaction SMQ occurring within 2 days after dosing during the combination, Part 1 period. This incidence rate is defined as number of subjects who experienced at least 1 AE in the MedDRA Anaphylactic Reaction broad scope SMQ with onset on the day of or within 2 days after any study therapy infusion during the combination period (Part 1) divided by number of treated subjects. For reference, the terms currently included in the MedDRA Anaphylactic Reaction SMQ based on MedDRA version 19.0 are listed in [Table 4.1-1](#).

The analysis of the primary endpoint will occur when all subjects who are still on-treatment complete Part 1 period.

**Table 4.1-1: Preferred Terms Included in the MedDRA Anaphylactic Reaction SMQ - Broad and Narrow Scopes**

Preferred Terma	Term Scopeb
Acute respiratory failure	Broad
Allergic oedema	Broad
Anaphylactic reaction	Narrow
Anaphylactic shock	Narrow
Anaphylactic transfusion reaction	Narrow
Anaphylactoid reaction	Narrow
Anaphylactoid shock	Narrow
Angioedema	Broad
Asthma	Broad
Blood pressure decreased	Broad
Blood pressure diastolic decreased	Broad
Blood pressure systolic decreased	Broad
Bronchial oedema	Broad
Bronchospasm	Broad
Cardiac arrest	Broad
Cardio-respiratory arrest	Broad
Cardio-respiratory distress	Broad
Cardiovascular insufficiency	Broad
Chest discomfort	Broad
Choking	Broad
Choking sensation	Broad
Circulatory collapse	Narrow
Circumoral oedema	Broad
Cough	Broad
Cyanosis	Broad
Dialysis membrane reaction	Narrow
Diastolic hypotension	Broad
Dyspnoea	Broad
Erythema	Broad
Eye oedema	Broad
Eye pruritus	Broad
Eye swelling	Broad
Eyelid oedema	Broad
Face oedema	Broad
Flushing	Broad
Generalised erythema	Broad

**Table 4.1-1: Preferred Terms Included in the MedDRA Anaphylactic Reaction SMQ - Broad and Narrow Scopes**

Preferred Terma	Term Scopeb
Hyperventilation	Broad
Hypotension	Broad
Injection site urticaria	Broad
Irregular breathing	Broad
Kounis syndrome	Narrow
Laryngeal dyspnoea	Broad
Laryngeal oedema	Broad
Laryngospasm	Broad
Laryngotracheal oedema	Broad
Lip oedema	Broad
Lip swelling	Broad
Mouth swelling	Broad
Nasal obstruction	Broad
Nodular rash	Broad
Ocular hyperaemia	Broad
Oedema	Broad
Oedema mouth	Broad
Oropharyngeal spasm	Broad
Oropharyngeal swelling	Broad
Periorbital oedema	Broad
Pruritus	Broad
Pruritus allergic	Broad
Pruritus generalised	Broad
Rash	Broad
Rash erythematous	Broad
Rash generalised	Broad
Rash pruritic	Broad
Respiratory arrest	Broad
Respiratory distress	Broad
Respiratory failure	Broad
Reversible airways obstruction	Broad
Sensation of foreign body	Broad
Shock	Narrow
Shock symptom	Narrow
Skin swelling	Broad
Sneezing	Broad

**Table 4.1-1: Preferred Terms Included in the MedDRA Anaphylactic Reaction SMQ - Broad and Narrow Scopes**

Preferred Term a	Term Scope b
Stridor	Broad
Swelling	Broad
Swelling face	Broad
Swollen tongue	Broad
Tachypnoea	Broad
Throat tightness	Broad
Tongue oedema	Broad
Tracheal obstruction	Broad
Tracheal oedema	Broad
Type I hypersensitivity	Narrow
Upper airway obstruction	Broad
Urticaria	Broad
Urticaria papular	Broad
Wheezing	Broad

a Changes may be made to this list with each new version of MedDRA. For information, the preferred terms defined at the time of finalization of the protocol are listed using MedDRA version 19.0.

b All Narrow Scope PTs are also included in the Broad Scope.

## 4.2 Secondary Endpoints

The safety- and PK-related secondary endpoints will be analyzed at the time of the first (primary) analysis when all participants who are still on-treatment complete Part 1 period. The efficacy-related secondary analysis will be analyzed at the time of final analysis when all patients have at least 9 months of follow-up.

### 4.2.1 MedDRA Anaphylactic Reaction Narrow Scope SMQ AE Incidence Rate

The first secondary endpoint is the incidence of AEs in the MedDRA Anaphylactic Reaction narrow scope SMQ occurring within 2 days after any study therapy infusion during the combination period (Part 1). This incidence rate will be defined similarly to the primary endpoint except that the event rate will be based on terms within the narrow scope SMQ rather than the broad scope.

### 4.2.2 Drug-Related Grade 3 - 5 AE Incidence Rate

The second secondary endpoint is the drug-related Grade 3 - 5 AE incidence rate defined using NCI CTCAE version 4.0 criteria. The drug-related Grade 3 - 5 AE rate is defined as number of subjects who experienced at least 1 AE of Grade 3 or higher, judged to be related to study drug by the investigator, and with onset on or after the first dose of study treatment and within 30 days of the last dose of study treatment, divided by number of treated subjects.

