Laboratory Tests	X	Beginning at Cycle 5 and every alternate dose thereafter (Cycle 7, 9, 11, 13, etc.), on-study local laboratory assessments should be done within 72 hours prior to dosing and include: CBC w/differential, LFTs (ALT, AST, total bilirubin, alkaline phosphatase), BUN or serum urea level, creatinine, corrected Ca, Na, K, Cl, LDH, glucose, amylase, lipase, phosphate, TSH with reflexive Free T4, Free T3. Beginning at Cycle 6 and every alternate dose thereafter (Cycle 8, 10, 12, 14, etc.), on-study local laboratory assessment should be done within 72 hours prior to dosing and include: LFTs (ALT, AST, total bilirubin, alkaline phosphatase) and creatinine.
Pregnancy Test (WOCBP only)	X	Serum or urine (minimum sensitivity equivalent units 25IU/L or equivalent units of HCG) every 4 weeks. A negative pregnancy test should be documented within 24 hours prior to start of each dose of investigational product.
Outcomes Research Assessments		
FACT-G, EQ-5D-3L, and FKSI-19	X	To be completed at the start of the clinic visit every 4 weeks from Cycle 5 onwards
Health Care Utilization	X	Health Care Utilization will be collected at each visit from Cycle 5 onwards

Table 2-3: On-Study Assessments - Part 2 (CA209800)

Procedure	For Part 2, Study treatment is Administered Every 4 Weeks (Both Arm A and Arm B)	Notes Cycle 5 will begin 6 weeks after Cycle 4
	Cycle 5 and beyond (Day 1)	
Pharmacokinetic and Immunogenicity Assessments		
Immunogenicity blood sample	X	Refer to Table 9.5-1
PK Samples	X	Refer to Table 9.5-1
Efficacy Assessment		
Tumor Assessment	See Notes	
First tumor assessment during Part 2 should occur after 8 weeks (\pm 1 week) relative to previous tumor assessment performed at Week 12.
 
Subsequent tumor assessments should occur every 8 weeks (\pm 1 week) for the first 12 months from randomization.
 
From the second year from randomization, tumor assessments should occur every 12 weeks (\pm 2 weeks) until disease progression or treatment discontinuation, whichever occurs later.
 
Contrast enhanced CT Chest, CT (or MRI with and without contrast) abdomen, pelvis and all known sites of disease. Use same imaging method as was used at screening/baseline.
 
Participants with a history of brain metastasis should have surveillance MRI brain with and without gadolinium approximately every 12 weeks, or sooner if clinically indicated (until disease progression or treatment discontinuation, whichever occurs later).

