7.1.2 Part 2 Study Treatment Administration

Starting 6 weeks after the last co-administered dose in Part 1, participants will be administered a flat dose 480 mg nivolumab 30-minute infusion every 4 weeks (Q4W) until unacceptable toxicity or disease progression is reached, whichever comes first.

Participants may be dosed up to 3 days after the scheduled date if necessary. Subsequent dosing should be based on the actual date of administration of the previous dose of drug. Every effort should be made to adhere to protocol treatment schedule of administration of nivolumab every 4 weeks in the maintenance phase. In extenuating circumstances in which the participant cannot make the dosing schedule within the 3-day window, BMS Medical Monitor should be contacted.

Note: Subjects who advance to Part 2 will be treated until progression or unacceptable toxicity, whichever comes first.

For details on prepared drug storage, preparation, and administration, please refer to the nivolumab, ipilimumab and BMS-986237 IBs and/or pharmacy reference sheets. The selection and timing of dose for each participant is as follows:

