7.4.3 Dose Discontinuation

The assessment for discontinuation of nivolumab should be made separately from the assessment made for discontinuation of ipilimumab. Although there is overlap among the discontinuation criteria, if discontinuation criteria are met for ipilimumab but not for nivolumab, treatment with nivolumab may continue if ipilimumab is discontinued. In this instance, the patient would be considered off part 1 of the study and must have a 6 weeks interval before moving on to part 2 of the study (nivolumab monotherapy).

If a participant in any of the nivolumab/ipilimumab combination arms meets criteria for discontinuation and investigator is unable to determine whether the event is related to both or one study drug, the participant should discontinue both nivolumab and ipilimumab and be taken off the treatment phase of the study.

Study treatment should be permanently discontinued for the following:

- Any Grade 2 drug-related uveitis, eye pain or blurred vision that does not respond to topical therapy and does not improve to Grade 1 severity within the re-treatment period OR requires systemic treatment
- Any Grade 3 non-skin, drug-related adverse event lasting $>$ 7 days, or recurs with the following exceptions for laboratory abnormalities, diarrhea, colitis, neurologic toxicity, drug-related

uveitis, pneumonitis, bronchospasm, myositis, myocarditis, rhabdomyolysis, hypersensitivity reactions, infusion reactions, and endocrinopathies:

- Grade 3 drug-related, diarrhea, colitis, neurologic toxicity, uveitis, pneumonitis, bronchospasm, myositis, myocarditis, rhabdomyolysis, hypersensitivity reaction, or infusion reaction of any duration requires discontinuation
- Grade 3 drug-related endocrinopathies, adequately controlled with only physiologic hormone replacement do not require discontinuation. Adrenal insufficiency requires discontinuation regardless of control with hormone replacement.
- Grade 3 drug-related laboratory abnormalities do not require treatment discontinuation except:
 - ◆ Grade 3 drug-related thrombocytopenia > 7 days or associated with bleeding requires discontinuation
 - ◆ Any drug-related liver function test (LFT) abnormality that meets the following criteria requires discontinuation:
 - Grade \geq 3 drug-related AST, ALT or Total Bilirubin requires discontinuation*
 - Concurrent AST or ALT > 3 x ULN and total bilirubin > 2x ULN

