9.2.1 Time Period and Frequency for Collecting AE and SAE Information

The collection of non-serious AE information should begin at initiation of study treatment until 100 days after the last dose of study therapy, at the timepoints specified in the Schedule of Activities ([Section 2](#)). Non-serious AE information should also be collected from the start of a placebo lead-in period or other observational period intended to establish a baseline status for the participants.

Sections 5.6.1 and 5.6.2 in the Investigator Brochure (IB) represent the Reference Safety Information to determine expectedness of serious adverse events for expedited reporting. Following the participant's written consent to participate in the study, all SAEs, whether related or not related to study treatment, must be collected, including those thought to be associated with protocol-specified procedures.

All SAEs must be collected that occur during the screening period and within 100 days of the last dose of study treatment. For participants randomized/assigned to treatment and never treated with study treatment, SAEs should be collected for 30 days from the date of randomization.

Admission for administration of anticancer therapy in the absence of any other SAEs (applies to oncology protocols)

Investigators are not obligated to actively seek AEs or SAEs in former study participants. However, if the investigator learns of any SAE, including a death, at any time after a participant has been discharged from the study, and he/she considers the event reasonably related to the study treatment or study participation, the investigator must promptly notify the sponsor.

The method of evaluating, and assessing causality of AEs and SAEs and the procedures for completing and reporting/transmitting SAE reports are provided in [Appendix 3](#).

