	
AE rate is defined as number of participants who experienced at least 1 AE of Grade 3 or higher, judged to be related to study treatment by the investigator, and with onset on or after the first dose of study treatment and within 30 days of the last dose of study treatment, divided by number of treated participants.
 
The third secondary endpoint is the all causality Grade 3 - 5 AE incidence rate defined using NCI CTCAE v 4.0 criteria. The all causality Grade 3 - 5 AE rate is defined as number of participants who experienced at least 1 AE of Grade 3 or higher with onset on or after the first dose of study treatment and within 30 days of the last dose of study treatment, divided by number of treated participants.
 
Safety related secondary endpoints will be analyzed at the time of the first (primary) analysis when all participants who are still on-treatment complete Part 1 period. The first secondary endpoint will be summarized using the same methods as described above for the primary endpoint analysis. The second secondary endpoint, on-treatment drug-related Grade 3 - 5 AEs occurring within 30 days after the last dose of study treatment, will be tabulated using worst grade per NCI CTCAE v 4.0 criteria by system organ class and preferred term by treatment arm. The third secondary endpoint, all causality Grade 3 - 5 AEs, will be summarized using similar methods as described for drug-related Grade 3 - 5 AEs.

[REDACTED]
	
[REDACTED]

For reference, the terms currently included in the MedDRA Anaphylactic Reaction SMQ based on MedDRA version 19.0 are listed in [Table 10.3.2-1](#).

Table 10.3.2-1: Preferred Terms Included in the MedDRA Anaphylactic Reaction SMQ - Broad and Narrow Scopes

Preferred Term	Term Scope
Acute respiratory failure	Broad
Allergic oedema	Broad
Anaphylactic reaction	Narrow
Anaphylactic shock	Narrow
Anaphylactic transfusion reaction	Narrow
Anaphylactoid reaction	Narrow
Anaphylactoid shock	Narrow
Angioedema	Broad
Asthma	Broad
Blood pressure decreased	Broad
Blood pressure diastolic decreased	Broad
Blood pressure systolic decreased	Broad
Bronchial oedema	Broad
Bronchospasm	Broad
Cardiac arrest	Broad
Cardio-respiratory arrest	Broad
Cardio-respiratory distress	Broad
Cardiovascular insufficiency	Broad
Chest discomfort	Broad
Choking	Broad
Choking sensation	Broad
Circulatory collapse	Narrow
Circumoral oedema	Broad
Cough	Broad
Cyanosis	Broad
Dialysis membrane reaction	Narrow
Diastolic hypotension	Broad
Dyspnoea	Broad

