#### **4.2.3 All Causality Grade 3 - 5 AE Incidence Rate**

The third secondary endpoint is the all causality Grade 3 - 5 AE incidence rate defined using NCI CTCAE version 4.0 criteria. The all causality Grade 3 - 5 AE rate is defined as number of subjects who experienced at least 1 AE of Grade 3 or higher with onset on or after the first dose of study treatment and within 30 days of the last dose of study treatment, divided by number of treated subjects.

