#### **6.1.2 Post Baseline Period**

On-treatment AEs will be defined as AEs with an onset date-time on or after the date-time of the first dose of study treatment (or with an onset date on or after the day of first dose of study treatment if time is not collected or is missing). An AE will be counted as on-treatment if the event occurred within 30 days (or 100 days depending on analysis) of the last dose of study treatment.

On-treatment evaluations (laboratory tests, pulse oximetry and vital signs) will be defined as evaluations taken after the day (and time, if collected and not missing) of first dose of study treatment. An evaluation will be counted as on-treatment if it occurred within 30 days (or 100 days depending on analysis) of the last dose of study treatment.

The Post Baseline Period may be further divided into the following sub-periods.

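### Both Grade 3-5 AE rates stop 30 days after the last dose, but the planned break before Part 2 is 42 days, so an AE on days 31-41 of the break counts only if a later dose is given

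*SAP*

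**What the plan says.** SAP 4.2.2 defines the drug-related Grade 3-5 rate from AEs "with onset on or after the first dose of study treatment and within 30 days of the last dose of study treatment". SAP 4.2.3 ends the all-causality rate at the same point: "within 30 days of the last dose of study treatment, divided by number of treated subjects". Protocol 10.3.2 agrees ("within 30 days of the last dose of study treatment, divided by number of treated participants"), as does Protocol Section 4. Under SAP 7.1, safety analyses use the combined Part 1 and Part 2 period unless otherwise noted, so the last dose may belong to either part.

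Protocol 7.1.2 schedules nivolumab maintenance "Starting 6 weeks after the last co-administered dose in Part 1". Under Protocol 7.4.3, the same 6-week wait applies when ipilimumab alone is stopped early and the participant moves to Part 2.

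SAP 6.1.2 leaves a choice of window for general on-treatment definitions. Its rule for evaluations reads "counted as on-treatment if it occurred within 30 days (or 100 days depending on analysis) of the last dose", and its AE rule offers the same two windows. The two Grade 3-5 endpoint definitions name only 30 days. Non-serious AEs are collected "until 100 days after the last dose of study therapy" (Protocol 9.2.1), and SAEs over the same period.

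**The concern.** A 30-day tail normally gives continuous cover during treatment, because doses are less than 30 days apart. Here one planned interval is longer than the tail. Within the uncovered stretch, whether an AE enters the endpoint depends on what happens after it starts.

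That dependence is not neutral. Protocol 7.4.3 requires permanent discontinuation for Grade 4 drug-related events. For a list of Grade 3 drug-related events that includes colitis, pneumonitis and myocarditis, it says that even an "infusion reaction of any duration requires discontinuation". Such an event late in the break can itself prevent the later dose that would have brought it into the count. The plan's research hypothesis is that the two regimens show no clinically relevant safety difference, so a rule that tends to leave out treatment-ending toxicity needs attention.

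**Working it through.** **The plan's own figure, for scale.** SAP Section 5 gives a 95% CI of (-16.7%, 16.7%) for 24% v 24% with 50 per arm. Check: 1.96 × √(2 × 0.24 × 0.76 / 50) = 0.167. It reproduces. It concerns the primary endpoint, and the point below does not rest on it.

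**Inputs.** Part 1 dosing every 21 days for 4 doses; Part 2 every 28 days; 6 weeks between them; endpoint tail 30 days; 50 treated participants per arm.

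**Timeline (day 0 = first dose).**
- Combination doses: days 0, 21, 42, 63.
- Cycle 5: 63 + 6 × 7 = day 105.
- Cover if dose 4 is the last dose: to 63 + 30 = day 93.
- Uncovered days before Cycle 5: break days 31 to 41, that is 41 - 30 = 11 days. This is 11/42 = 26% of the break, or 11/105 = 10% of the scheduled time before Cycle 5.
- With the ±3-day window for Part 2 dosing in Protocol 7.1.3, the break is 39 to 45 days and the uncovered stretch 8 to 14 days.
- Neither of the other planned intervals (21 and 28 days) exceeds 30.

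**The rule applied** (counted if onset ≤ last dose + 30):

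| Onset, break day | Dose 4 was the last dose | Cycle 5 given on day 105 |
|---|---|---|
| 30 | counted | counted |
| 31 | not counted | counted |
| 35 | not counted | counted |
| 41 | not counted | counted |

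With a 100-day tail, all eight cells read counted.

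**First analysis.** Both endpoints are analysed when participants still on treatment have completed Part 1 (SAP 4.2), about 3 months after accrual ends (SAP Schedule of Analyses). Completing Part 1 does not require a Part 2 dose. Three months is 3 × 30.4375 = 91 days, and 91 - 63 = 28. A participant first dosed on the last day of accrual would then be on about break day 28, and one first dosed 3 to 13 days earlier on break days 31-41. For these earlier participants, dose 4 is still the last dose, so an AE already recorded on days 31-41 is outside the window whatever follows.

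**Size (assumed, since the documents give no Grade 3-5 rate over time).** Let m be the monthly risk of a first Grade 3-5 event and s the share of such events not followed by a later dose. The loss among those reaching dose 4 is [1 - (1 - m)^(11/30.4375)] × s.
- m = 2%, s = 25%: 0.18%, or 0.09 participants per 50.
- m = 5%, s = 50%: 0.92%, or 0.46 per 50.
- m = 10%, s = 100%: 3.74%, or 1.87 per 50.

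Each participant moves an arm's rate by 1/50 = 2 points. Fewer than 50 per arm are likely to reach dose 4, so these figures lean high.

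**The case against.** The strongest reply is that the gap is narrow and partly covered elsewhere. All AEs in the 30 days after dose 4 are counted, whether or not they end treatment. Deaths, SAEs and AEs leading to discontinuation have their own analyses (SAP 7.6.4 to 7.6.6), so the documents do not show that these events go unreported; they miss only the two headline rates. SAP 7.6.3 refers the analysis to a Core Safety SAP that is not among the documents and may add a 100-day display. Dose, schedule, break and rule are the same in both arms, and everything is descriptive with no p-values. All of this stands and limits the size. It does not remove the point, because the endpoint definitions themselves fix 30 days.

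Some stronger readings are tempting but are not supported:
- *Treatment-ending events are dropped and tolerated ones kept.* The condition is whether any later dose was given. A tolerated event is also lost if the participant stops for progression, and an event that ends treatment only after Cycle 5 is counted.
- *A fatal AE starting late in the break can never count.* It is certain to be lost only if the participant dies before Cycle 5.
- *A Grade 3 asymptomatic lipase rise on day 40 would be counted while colitis is not.* Under Protocol 9.2.6 such a result need not be reported as an AE at all.
- *The laboratory analyses share the fault.* The Cycle 5 panel does fall late in the break ("on-study local laboratory assessments should be done within 72 hours prior to dosing"). However, no laboratory endpoint is defined and SAP 6.1.2 allows 100 days.

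**Conclusion.** The point holds for both Grade 3-5 secondary endpoints. As written, an AE on break days 31-41 is counted only if a later study dose is given, and not if none has been given by the data cut. Because discontinuation follows from Grade 4 and several Grade 3 drug-related events, the loss falls mainly on the most serious events, and both rates are somewhat understated.

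A reader might infer that the comparison between arms is biased towards no difference. The documents do not establish that: the difference is distorted only if events in this stretch, or stopping, differ by arm.

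The size rests wholly on assumed event and stopping rates and is probably small, about 0 to 2 participants per 50. The primary endpoint, with its 2-day window, and the sample size are unaffected. This is an inexpensive improvement to a definition and does not threaten the trial's main conclusion.

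**What to change.** In SAP 4.2.2 and 4.2.3 and Protocol Sections 4 and 10.3.2 (with the matching synopsis text), make the window independent of whether Part 2 is given:
- When the last dose received is the combination dose that precedes the planned 6-week interval, count AEs through day 45 after it (42 days plus the 3-day visit window), in both arms. That dose is dose 4, or an earlier last combination dose where a move to Part 2 is planned under Protocol 7.4.3.
- Keep 30 days for every other last dose. Participants who stop after doses 1 to 3 with no planned 6-week interval should not receive the longer window.
- Keep the plain 30-day rate as a supportive display.
- State in SAP 7.6.3 that this definition takes precedence over the Core Safety SAP for these two endpoints.

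Alternatively, also report both endpoints with the 100-day window already in SAP 6.1.2. The day-45 rule leaves some dependence when Part 2 is delayed past day 45, which Protocol 7.4.3 can allow; the 100-day display covers those days up to day 100.

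Cost: wording and one derivation. No new data are needed, since AEs are already collected for 100 days. The reported rates may be slightly higher and will depart a little from the sponsor's standard 30-day display.
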